8.5. Secondary Efficacy Analysis

Analysis of the time to event outcomes will include all randomised patients. All analysis for other secondary endpoints will be based on ‘intention to treat’ population.

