5.2. Primary Efficacy Variable

Proportion of patients with intensification of LLT relative to baseline, regardless of adherence to the DSS, within 16 weeks of index ACS event.

Intensification includes:

- escalation of monotherapy OR
- initiation of combination therapy OR
- escalation of combination therapy

Only commercially available licensed LLT will be considered.

Patients will be considered LLT-naïve on admission if no LLT medications (statins, ezetimibe, bempedoic acid, bile acid sequestrants, evolocumab, alirocumab and inclisiran) are listed on the LLT 'prior to admission' form which captures LLT therapy in the month prior to admission. Patients who are admitted on medicines such as fish oils, nicotinic acid derivatives and fibrates will be considered to be a subgroup of LLT-naïve patients since these agents do not have a clinically significant effect on LDL levels.

Patients who are LLT-naïve on admission will be expected to start on statin monotherapy prior to discharge or an alternative monotherapy prior to discharge, and rarely post-discharge i.e. during follow up. For patients initiated on monotherapy as their first LLT, intensification of therapy in these patients can only occur after starting monotherapy. Therefore, the primary outcome will be met in these patients if they subsequently receive escalation of their monotherapy or start combination therapy during follow up. It is also possible that some LLT-naïve patients may be started on combination therapy at discharge. In this case the primary outcome will be met at discharge.

For patients who are already prescribed LLT prior to admission, they will meet the primary outcome if intensification occurs between admission and discharge or after discharge.

Table 2: Primary outcome definition

Baseline therapy patients recruited with	Meets primary outcome at 16 weeks if the patients is now on
<2 LLT drugs (i.e. 0 to 1)	Combination therapy (2 or more drugs) OR
	Escalated monotherapy (one drug increase in dose, or switch to more potent single drug)

Imperial Clinical Trials Unit	ZODIAC STATISTICAL ANALYSIS PLAN – MAIN ANALYSIS	V1 17 th Jan 2024
-------------------------------	--	------------------------------

>=2 LLT drugs	Escalated combination therapy (e.g. 3 drugs, increase in the potency of one of the drugs if the total number of drugs remains unchanged)
---------------	--

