8.4. Primary Efficacy Analysis

The primary outcome measure, the proportion of patients treated with combination therapy, or who receive escalated monotherapy, or escalated combination therapy, within 16 weeks of the index ACS (regardless of adherence at 16 weeks) will be modelled using a generalised linear mixed model. This model will use a binomial distribution, log link function and with fixed effect for country and site type (secondary/tertiary care/mixed) and a random effect for study site (as a random intercept). If there is a convergence problem with the log-binomial model, Poisson regression with robust standard errors (modified Poisson regression) will be used. The intervention effect will be reported as a Risk Ratio with a 95% confidence interval. For primary analysis hypotheses will be tested as two-sided with a significance level of 0.05.

$$\log(\pi_{ij}) = \beta_0 + \beta_1 ACSDSS_{ij} + \beta_2 COUNTRY1_{ij} + \beta_3 COUNTRY2_{ij} + \beta_4 Site\ type_{ij} + \beta_5 Site\ type_{ij} + U_j$$

Where:

Imperial Clinical Trials Unit	ZODIAC STATISTICAL ANALYSIS PLAN – MAIN ANALYSIS	V1 17 th Jan 2024
-------------------------------	--	------------------------------

- π_{ij} : probability of combination therapy for the i^{th} patient in j^{th} site
- $ACSDSS_{ij}$: dummy variable for intervention ($ACSDSS_{ij} = 0$ or 1) for patient i in j^{th} site
- $COUNTRY1_{ij}, COUNTRY2_{ij}$: dummy variable for COUNTRY ($COUNTRY_{ij} = 0$ or 1) for patient i in j^{th} site
- $Site\ type1_{ij}, Site\ type2_{ij}$: dummy variable for Site Type ($Site\ type_{ij} = 0$ or 1) for patient i in j^{th} site type
- U_j : random effect for site $j \sim N(0, \sigma_u^2)$

This model will use the modified intention-to-treat population and will include all eligible and randomised patients through use of multi-level multiple imputation. If any participants die within 16 weeks they will be excluded from this primary analysis and any similar secondary outcome analysis but will be included in the time to event outcomes (until censored). We will tabulate mortality by intervention arm.

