We define the primary outcome as missing for anyone who does not have full 16 week follow up, unless they have met the primary outcome prior to the time they are lost to follow up. All patients will be followed up and the primary outcome data will be collected unless the participant requests to withdraw from data collection. Missing data will be examined and quantified; this will include the time of withdrawal and tabulation for reasons for non-completion of study by country, site, and arms. Patterns of missingness and relationship between variables and outcome will be explored. The proportion of clusters (sites) with a missing individual outcome will be calculated and reported as the number of entire clusters with a missing outcome divided by the number of clusters randomised.

As mentioned in Section 4.8, some patients may have data reported at 24 weeks only. These data may be used, where appropriate, to derive or impute the LLT medication status at 16 weeks.

Although mixed models are valid under the missing at random (MAR) assumption, we will use the multilevel multiple imputation (MMI) method to impute values for individuals who have missing outcome data. Missing data can be related to the cluster level or at patient level. We define level 1 variables as those relating to the patient as X and Y and Z, and level 2 variables as those relating to the site as A and B.

Using the *JOMO package* in R with missing outcome data we can use an imputation model which is the same as the analysis model. The JOMO package allows imputation on a mix of multilevel continuous and categorical data.¹⁵ This method uses Markov chain Monte Carlo (MCMC) methods to impute missing values. We will run N imputations and combine the estimates using the mitools package. We will impute N datasets based on the percentage of participants with incomplete outcomes, where N is rounded to the nearest 10. A minimum of 5 imputation datasets will be used. We will include at patient level, intervention, outcome,

Imperial Clinical Trials Unit	ZODIAC STATISTICAL ANALYSIS PLAN – MAIN ANALYSIS	V1 17 th Jan 2024
-------------------------------	--	------------------------------

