8.5.3. Binary outcomes

- Proportion of patients' reaching target LDL-C levels, <1.4 mmol/L (<55 mg/dL) by Week 16, proportion of patients who receive combination therapy, proportion of patients who receive escalated monotherapy and proportion of patients who receive escalated combination therapy

This analysis will be for all people with Week 16 follow-up.

We will follow the same approach as described for primary outcome and use log-binomial model or modified Poisson regression with a fixed effect for country and site type (secondary/ tertiary care/mix of both) and a random effect for study site (as a random intercept) to estimate an adjusted Risk Ratio with a 95% confidence interval and p-value.

Imperial Clinical Trials Unit	ZODIAC STATISTICAL ANALYSIS PLAN – MAIN ANALYSIS	V1 17 th Jan 2024
-------------------------------	--	------------------------------

Model assumptions for all models will be examined using residual analysis. Following the recommendations by Parker¹⁶ and Rubin¹⁷ no adjustments for multiple testing will be used but a precise, focused interpretation of the individual results for secondary outcomes will be reported.

$$\log(\pi_{ij}) = \beta_0 + \beta_1 ACSDSS_{ij} + \beta_2 COUNTRY1_{ij} + \beta_3 COUNTRY2_{ij} + \beta_4 Site\ type_{ij} + \beta_5 Site\ type_{ij} + U_j$$

Where:

- π_{ij} : probability of combination therapy (or other binary outcome) for the i^{th} patient in j^{th} site
- $ACSDSS_{ij}$: dummy variable for intervention ($ACSDSS_{ij} = 0$ or 1) for patient i in j^{th} site
- $COUNTRY1_{ij}, COUNTRY2_{ij}$: dummy variable for COUNTRY ($COUNTRY_{ij} = 0$ or 1) for patient i in j^{th} site
- $Site\ type1_{ij}, Site\ type2_{ij}$: dummy variable for Site Type ($Site\ type_{ij} = 0$ or 1) for patient i in j^{th} site type
- U_j : random effect for site $j \sim N(0, \sigma_u^2)$

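### The SAP states conflicting analysis sets for the four secondary binary outcomes, and its Week 16 follow-up rule drops observed successes that the primary analysis keeps

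*SAP*

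**What the plan says.** The four outcomes are the LDL-C target below 1.4 mmol/L, combination therapy, escalated monotherapy and escalated combination therapy (SAP 5.3, items 7 to 10). Three places in the SAP say who is analysed:

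- Section 8.5, for every secondary endpoint except time to event: "All analysis for other secondary endpoints will be based on" the intention-to-treat population.
- Section 8.4: "If any participants die within 16 weeks they will be excluded from this primary analysis and any similar secondary outcome analysis".
- Section 8.5.3: "This analysis will be for all people with Week 16 follow-up". Its next paragraph says "We will follow the same approach as described for primary outcome" and goes straight on to describe the regression model.

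For the primary outcome, section 8.4 says: "This model will use the modified intention-to-treat population and will include all eligible and randomised patients through use of multi-level multiple imputation". A patient without full 16-week follow-up has a missing primary outcome, "unless they have met the primary outcome prior to the time they are lost to follow up". The outcome can be met early. Of an LLT-naive patient started on combination therapy at discharge, section 5.2 says: "In this case the primary outcome will be met at discharge".

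Section 7.1 is headed as the intention-to-treat population but defines the modified set (mITT), which leaves out deaths. Sections 7.1 and 8.10 name a separate full ITT analysis that includes them. Section 8.5.2 imputes missing lipid values at 16 weeks.

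**The concern.** Each of the four outcomes is to be reported with a risk ratio, a confidence interval and a p-value. Two statisticians who both follow the SAP could analyse different patients and report different denominators.

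The 8.5.3 rule also separates the therapy-type outcomes from the composite they are meant to explain. Secondary objective 4 asks which kind of intensification patients received. A patient intensified at week 4 and lost at week 10 would be a success in Table 23 but would not appear in Tables 27 to 29. A complete-case analysis has only sensitivity status for the primary outcome (8.10), yet for these outcomes a similar restriction becomes the main analysis, with no reason given.

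Week 16 follow-up is not defined either. Section 4.1 says there are no defined visits after baseline, so the membership of this set is open to interpretation.

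**Working it through.** **1. The plan's own figures (SAP 4.5).** Inputs: 5% versus 15%, 90% power, two-sided 5%, ICC 0.1, 31 patients per site, 24 sites per arm, 5% loss.

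- Design effect: 1 + (31 − 1) × 0.1 = 4.
- Individually randomised size per arm: 188 (pooled variance) or 183.9 (unpooled). Times 4: 752 or 736. The stated 744 = 24 × 31 lies between them.
- Loss: 744 / 0.95 = 783.2, rounded up to 784 per arm, so 1568 in total. Then 33 × 24 = 792 per arm, so 1584 in total.

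The sample size reproduces and is not in dispute.

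**2. How many patients each rule admits.** With 1584 recruited and 5% lost, 1584 × 0.05 = 79.2. The SAP gives no mortality rate, so 1% to 5% is assumed.

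| Rule | Arithmetic | N |
|---|---|---|
| Full ITT | 1584 | 1584 |
| Deaths excluded, remainder imputed | 1584 × 0.99 to 1584 × 0.95 | 1568 to 1505 |
| Week 16 follow-up only | 1584 × 0.94 to 1584 × 0.90 | 1489 to 1426 |

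The two outer rules differ by 95 to 158 patients. The last two rules differ only by the 79 who are lost.

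**3. The same patient under each rule.** Take a survivor who escalated monotherapy at week 4 and was lost at week 10.

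- Primary outcome (8.4): observed, counted as a success.
- Escalated monotherapy under mITT with the 8.4 rule: observed, counted as a success.
- Escalated monotherapy under 8.5.3: not in the analysis.

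Section 8.4 itself separates having full follow-up from having met the outcome before loss. An early success therefore does not amount to Week 16 follow-up.

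**4. How many observed successes are dropped.** Lost per arm: 792 × 0.05 = 39.6. Assume loss is unrelated to outcome. The maximum arises if every success among lost patients came before the loss.

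- At 5% and 15%: 39.6 × 0.05 = 2.0 (SoC) and 39.6 × 0.15 = 5.9 (DSS). If only a quarter came before the loss: 0.5 and 1.5.
- The SAP's 5% and 15% refer to combination therapy, and the composite is wider. At assumed rates of 40% and 50% the maxima are 15.8 and 19.8.

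**5. If loss depends on outcome (assumption).** Let half of successes be early, with 20% of those lost and 5% of everyone else lost. The completer proportion is p(0.5 × 0.80 + 0.5 × 0.95) / [p(0.5 × 0.80 + 0.5 × 0.95) + 0.95(1 − p)].

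- p = 0.05: 0.04375 / 0.94625 = 4.6%.
- p = 0.15: 0.13125 / 0.93875 = 14.0%.

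Both proportions fall, but the risk ratio is almost unchanged (3.02 against 3.00), because the same loss pattern was assumed in both arms.

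**6. LDL-C.** Section 8.5.2 imputes the Week 16 value from baseline and earlier measurements. Section 8.5.3 then takes the below-1.4 target only in people followed to Week 16. One laboratory variable therefore has two analysis sets.

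**The case against.** Several parts of the case against this point stand.

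- **The number of populations.** A reader might count three incompatible sets. That depends on reading section 8.5 as the full ITT. If it points to section 7.1, whose heading it echoes, it agrees with the exclusion of deaths in 8.4 and two rules remain in conflict. The conflict with 8.5.3 survives either reading.
- **Contradiction inside 8.5.3.** The reference to the primary approach runs directly into the model specification and may mean only the model. Section 8.5.3 does not mention imputation. On that reading it contradicts 8.5 rather than itself.
- **Selection on attendance.** A reader might infer that the rule selects patients who attend, and that attendance goes with treatment change. The documents do not show this. Section 4.8 sends sites to the medical record or the GP when visits are missed.
- **Components not summing to the composite.** They need not sum even with complete data. Section 5.2 counts any qualifying change at any time, so one patient can have two types. Item 8 of section 5.3 speaks of receiving combination therapy; read literally, that could include patients already on it at baseline.
- **Priority.** Section 9.2 calls secondary results hypothesis-generating, and the primary analysis is untouched.

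It could also be argued that 8.5.3 governs because it is the more specific text. That settles the denominator, but it leaves observed successes out of the therapy-type outcomes.

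**Conclusion.** The point holds as a conflict over analysis sets, together with a stated rule in 8.5.3 that discards observed therapy-type successes and splits the LDL-C target from LDL-C. It should be corrected before the analysis, but it does not threaten the primary result.

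At the planned loss the size is modest. About 79 of 1584 patients have their inclusion depend on the rule. At most about 2 (SoC) and 6 (DSS) observed successes are dropped, given loss unrelated to outcome and rates of 5% and 15%.

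Two stronger readings are not supported. The 79 are all the patients expected to be lost, not the number of dropped successes. Deaths do not add to the early-success mismatch, because the primary analysis excludes them as well; they matter only to the choice between full ITT and mITT.

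**What to change.** - In section 8.5, name one population for the four binary outcomes: the mITT set of the primary outcome, with deaths handled in the same way. Remove the sentence in 8.5.3 that restricts them to people with Week 16 follow-up, or make that restriction a sensitivity analysis with Week 16 follow-up defined.
- Apply the 8.4 missing-data rule to each therapy type separately. A type met before loss counts as observed; a type not yet met at loss is missing.
- Impute what is missing with the therapy types added to the imputation model, and state a consistency rule: a composite of No implies No for every type, and a composite of Yes implies at least one qualifying type. First settle whether the combination-therapy outcome means initiated or simply received, since only the former is a component of the composite.
- Derive the LDL-C target from the LDL-C values imputed under 8.5.2.
- State in Tables 27 to 30 which set N refers to.

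The cost is SAP wording plus a modest extension of the imputation model. The present specification for LLT outcomes (8.4 and 14.3) imputes only the primary outcome, so the additional imputations would have to be programmed and checked. No further data or patients are needed.

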8.5.1. Time to event outcome

- Time to initiation of combination therapy: the start defined as date the participant entered the trial (consent date) and end defined as date of initiation of combination therapy or escalation of therapy. We will censor for loss to follow up, withdrawals and death.

Kaplan-Meier plots will be used to estimate and display time to event outcomes such as time to intensification of LLT by study arms. A **Cox proportional hazards model with shared frailty** will be used to account for clustering and to assess the effect of DSS or SoC after adjusting for stratification factors. We will report adjusted hazard ratio (HR) and 95% confidence interval with p-value.

$$\log \left(\frac{h(t)}{h_0(t)} \right) = \beta_1 ACSDSS_{ij} + \beta_2 COUNTRY1_{ij} + \beta_3 COUNTRY2_{ij} + \beta_4 Site\ type_{ij} + \beta_5 Site\ type_{ij} + U_j$$

Where:

- $\log \left(\frac{h(t)}{h_0(t)} \right) =$: log hazard ratio
- $ACSDSS_{ij}$: dummy variable for intervention ($ACSDSS_{ij} = 0$ or 1) for patient i in j^{th} site
- $COUNTRY1_{ij}, COUNTRY2_{ij}$: dummy variable for COUNTRY ($COUNTRY_{ij} = 0$ or 1) for patient i in j^{th} site
- $Site\ type1_{ij}, Site\ type2_{ij}$: dummy variable for Site Type ($Site\ type_{ij} = 0$ or 1) for patient i in j^{th} site type
- U_j : random effect for site $j \sim N(0, \sigma_u^2)$

Imperial Clinical Trials Unit	ZODIAC STATISTICAL ANALYSIS PLAN – MAIN ANALYSIS	V1 17 th Jan 2024
-------------------------------	--	------------------------------

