8.3. Baseline Demographics

Baseline patient characteristics will be cross tabulated according to the randomised group to check for appropriate balance and to provide an overview of the study population. They will be summarised using means and standard deviations or medians and 25th, 75th percentiles for continuous variables, and counts and percentages for categorical variables.

As described in Section 5.2, baseline LLT is defined as LLT prior to admission and will be categorised as none, LLT monotherapy and LLT combination therapy. Combinations will be further classified by number of LLT drugs. In addition, we will present LLT classified by intensity based on expected percentage reduction in LDL-C as categorised in the 2019 ESC/EAS guidelines for the management of dyslipidaemias.¹ An additional category of ‘very high intensity’ is included starting at 65% LDL-C reduction. This is just above the 64% LDL-C reduction of evolocumab 140/420mg, the highest expected LDL-C reduction associated with a monotherapy medication in the ZODIAC study. Combination therapies typically are classified as moderate intensity or higher.

For lipid levels, the baseline value will be defined as the last value recorded before or at the day of hospital admission for ACS whichever is the closest to the day of hospital admission.

No hypothesis testing will be performed to test for differences in baseline characteristics by arm.

We will also examine balance between trial arms for the stratification variables at the cluster level.

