12.1. Recruitment

Table 7: Randomisation stratification variables

		Number of Sites		
		DSS	Control	Overall
Sites, N (%)	United Kingdom			
	Italy			
	Spain			
	Total			
Clinic Type, N (%)	Secondary care			
	Tertiary care			
	Mix of both			
	Total			

Table 8: Number of patients per site per country

		Total N
Total Patients		
Centre	Name of site	N (%)
United Kingdom	...	
	...	
	...	
Italy	...	
	...	
	...	
Spain	...	
	...	
	...	

Imperial Clinical Trials Unit	ZODIAC STATISTICAL ANALYSIS PLAN – MAIN ANALYSIS	V1 17 th Jan 2024
-------------------------------	--	------------------------------

Table 9: Reasons for exclusion of sites

Exclusion reason (patients)	N (%)
Unable to capture/ provide data on patients with ACS during admission and follow up	
Unable or unwilling to use lipid lowering treatments other than statins for ACS care	
Unable or unwilling to access and undertake training for the DSS	
Inadequate internet connection at site and the ability to access the DSS	
Site did not proceed	

Table 10: Reasons for exclusion of participants from enrolled sites

Exclusion reason (patients)	N (%)
Aged <18 to ≥ 80 years old	
Unable to provide written informed consent	
Patient rescinded consent (changed mind before any data collected)	
LDL-C measurement < 1.8 mmol/L at admission	
Unstable angina	
ACS event not verified in time	
>72 hours after ACS event	

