14.2. Secondary Outcomes

14.2.1. Time to event

```
// Load the data
use "datafile.dta", clear

// Set up date as survival data
stset outcome_date , failure(outcome=1) origin(date of consent)

// Fit the Cox proportional hazards model with shared frailty
stcox intervention country site_type, shared(site) frailty(site)

// Summarize the model results
estat phtest
```

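### Time to intensification is counted from consent, but the events it counts can occur from admission, so changes on or before the consent day have no positive analysis time

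*SAP*

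**What the plan says.** Section 8.5.1 of the SAP defines the origin of the time-to-event outcome with "the start defined as date the participant entered the trial (consent date"). For the other limit of the interval, the same section has "end defined as date of initiation of combination therapy or escalation of therapy". Appendix D, section 14.2.1, repeats the origin in the example code: "stset outcome_date , failure(outcome=1) origin(date of consent"). Censoring is given for loss to follow-up, withdrawal and death. There is no rule for events on or before the origin and no administrative cut-off at 16 weeks. Section 8.5 adds: "Analysis of the time to event outcomes will include all randomised patients".

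The event itself is defined in section 5.2, whose window is 16 weeks from the index ACS event. Of patients already on lipid-lowering therapy (LLT), it says "they will meet the primary outcome if intensification occurs between admission and discharge or after discharge". Of LLT-naïve patients started on a combination at discharge, it says "In this case the primary outcome will be met at discharge". The reference treatment is fixed in section 8.3: "baseline LLT is defined as LLT prior to admission". Table 10 in section 12.1 lists ">72 hours after ACS event" among the reasons for excluding participants, so enrolment some days after the event is foreseen.

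**The concern.** The primary outcome and the first-listed secondary outcome describe the same treatment change on two clocks. A patient whose therapy is stepped up on the day of admission and who consents on a later day meets the primary outcome, yet has a negative survival time. A patient whose therapy is changed on the day of consent has a survival time of zero. Neither can belong to a risk set that opens after time zero.

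At stake is whether the analysis of speed of intensification covers the patients it claims to cover. Those lost all have events, and they are the earliest ones. Table 1 in section 4.8 puts consent and the DSS variables in the same Baseline visit, so some consent-day changes may be exactly the fast responses to the DSS that this outcome is meant to detect. If no rule is set in advance, one will have to be chosen once the dates are visible.

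**Working it through.** **1. The two clocks side by side**

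| Element | Primary outcome | Time to intensification |
|---|---|---|
| Origin | Index ACS event (5.2) | Consent (8.5.1, 14.2.1) |
| Reference treatment | LLT before admission (8.3) | Same event, so the same reference |
| Earliest counted change, already on LLT | From admission (5.2) | Not restricted to after consent |
| Earliest counted change, naïve and started on a combination | At discharge (5.2) | Not restricted to after consent |
| Patients | Deaths excluded (8.4) | All randomised (8.5) |

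Analysis time = event date − consent date. A change before consent gives time < 0; a change on the consent day gives time = 0. Stata's `stset` leaves out records that end at or before the origin, so both groups drop out under the line as written. Nothing in the supplied text requires consent to precede the first in-hospital change.

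**2. The plan's own figure**

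The SAP gives no event count, hazard ratio or power for this outcome. Its sample size (section 4.5) supplies rates and an arm size for illustration, and it reproduces:

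- Unpooled formula: (1.960 + 1.282)² × (0.05×0.95 + 0.15×0.85) / 0.10² = 183.9 per arm.
- Design effect: 1 + (31 − 1)×0.1 = 4, giving 735.5 per arm.
- 735.5/31 = 23.7 clusters, rounded up to 24; 24×31 = 744, as stated.

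**3. Illustration at the SAP's rates**

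Inputs: 744 per arm and rates of 5% and 15% (section 4.5, where they refer to combination therapy only). The share of events falling on or before the consent day is **assumed**; the documents give none. With e events and d dropped in an arm, the remaining risk is r = (e − d)/(744 − d). The cumulative-hazard ratio is ln(1 − r_DSS)/ln(1 − r_SoC).

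All events kept: e = 37.2 and 111.6, total 148.8; ln(0.85)/ln(0.95) = 3.17.

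| Assumed share dropped, SoC / DSS | Events dropped, SoC / DSS | Events left | Remaining risk, SoC / DSS | Ratio |
|---|---|---|---|---|
| 10% / 10% | 3.7 / 11.2 | 133.9 | 0.0452 / 0.1371 | 3.19 |
| 30% / 30% | 11.2 / 33.5 | 104.2 | 0.0355 / 0.1099 | 3.22 |
| 50% / 50% | 18.6 / 55.8 | 74.4 | 0.0256 / 0.0811 | 3.26 |
| 10% / 30% | 3.7 / 33.5 | 111.6 | 0.0452 / 0.1099 | 2.52 |
| 30% / 50% | 11.2 / 55.8 | 81.8 | 0.0355 / 0.0811 | 2.34 |
| 30% / 60% | 11.2 / 67.0 | 70.7 | 0.0355 / 0.0659 | 1.89 |

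**4. A commoner event**

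The composite also counts escalation, so it may be more frequent than 5% and 15%. Assume 30% in SoC and 40% in DSS:

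- All events kept: ln(0.60)/ln(0.70) = 1.43.
- Nine percentage points lost in each arm: risks 21/91 and 31/91, ratio 1.59.
- Nine points lost in SoC and 15 in DSS: risks 21/91 and 25/85, ratio 1.33.

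The ratio can move either way from 1.43.

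**The case against.** The best counter-arguments are these.

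- **The SAP never says that these patients are excluded.** True. The exclusion is inferred from how the software treats a line that is offered as example code and contains a placeholder rather than a variable name. Table 25 reports N and n by arm, so a loss would be visible. Even so, a non-positive time cannot contribute to a risk set, and the text gives no rule for it.
- **Negative times depend on an event date that the SAP leaves open.** Section 5.2 derives the outcome by comparing the prior-to-admission, discharge and follow-up forms. If in-hospital changes are dated at discharge, negative times would be rare and mainly same-day ties would remain. This stands as a limit on size. The wording of 8.5.1 points to the actual start of the new therapy, but the Appendix A algorithm is an embedded file that is not in the supplied text.
- **Consent is a natural origin, because the DSS cannot have been applied to a patient in the trial before then.** That would support a different endpoint, counting only changes after consent. It does not fit an event defined from admission against pre-admission therapy.

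A reader might go further and infer that the hazard ratio will be exaggerated, because pre-consent changes should be equally common in both arms. The documents do not support this. Consent-day changes may result from DSS use and be more frequent in that arm. DSS-site staff are also trained before recruitment starts (section 4.1), so equality before consent is itself an assumption. Nor would a gap between this hazard ratio and the primary risk ratio prove distortion: in the 30% versus 40% example the two are 1.43 and 40/30 = 1.33 with nothing deleted.

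**Conclusion.** The mismatch is in the current text and code. As written, the rule gives some patients who meet the primary outcome an unusable survival time, contrary to the statement that all randomised patients are included.

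The number of such patients cannot be derived, because the timing of consent relative to in-hospital prescribing is not given. The direction of bias is also unknown. At the SAP's rates, equal proportional losses mainly cost events and raise the ratio slightly (3.17 to at most 3.26), whereas losses concentrated in the DSS arm pull it toward 1 (1.89 to 2.52 in the cases shown). These figures rest on assumed shares and are not forecasts.

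This should be fixed before analysis, but it is not critical. It concerns one secondary outcome, and section 9.2 treats secondary results as hypothesis-generating. A reader might infer that the primary result is compromised too; it is not, since the primary outcome is binary and does not use the consent date. Much of the protocol is absent from the supplied text, so a rule there cannot be ruled out; the supplied SAP text contains none.

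**What to change.** In section 8.5.1 and the code in section 14.2.1:

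1. Start the clock at the primary outcome's origin. That is the index ACS event as section 5.2 stands; index admission would also serve if the SAP names it for both analyses.
2. State which date is the event date for an in-hospital change: the start of the new therapy or discharge.
3. Give day-0 events a small positive time, for example 0.5 day.
4. Censor administratively at 16 weeks from that origin. This also settles how 24-week records (sections 4.8 and 8.4) enter this outcome.
5. Report, by arm, the number of counted changes before consent and on the consent day.

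A sensitivity analysis restricted to changes on or after the consent day is optional. If consent is kept as the origin instead, a written rule for times at or below zero is the minimum.

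The cost is a few sentences of SAP text, one code line and one small table. The dates should largely be to hand, since deriving the primary outcome already requires placing treatment changes within its window. The sample size does not change.
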